5.4.5 Marked changes in vital signs

A marked increase is defined as:

- Systolic Blood Pressure >150 mmHg and increase ≥ 25 mmHg above baseline
- Diastolic Blood Pressure >90 mmHg and increase ≥ 10 mmHg above baseline
- Pulse Rate >100 bpm and increase ≥ 10 bpm above baseline

A marked decrease is defined as:

- Systolic Blood Pressure <100 mmHg and decrease >10 mmHg below baseline
- Diastolic Blood Pressure <60 mmHg and decrease >10 mmHg below baseline
- Pulse Rate <60 bpm and decrease >10 bpm below baseline

6. GENERAL ANALYSIS DEFINITIONS

6.1 TREATMENTS

For the definition of treatment administered during the trial, see Section 4 of CTP.

Note: the last day of each of the periods is excluded from the respective period. It defines the first day of the subsequent period.

- Screening: From informed consent to randomisation
- Post-randomisation (optional^[a]): From randomisation to first trial drug intake in treatment period.
- Treatment period: From first trial drug intake (or re-start of treatment if interruption) to last trial drug intake (or the day before start date of interruption if interruption) plus one day
- Off-treatment (optional^[a]): From start date of interruption to re-start of treatment
- Residual effect period^[b]: From the last trial drug intake plus one day to last trial drug intake plus 28 days plus one day or to date of first trial drug intake in extension trial, whichever occurs earliest
- Follow-up (optional^{[a][b]}): From last trial drug intake plus 29 days up to the beginning of post-study period. This period is only created if last trial drug intake took place more than 28 days before trial completion, or for patients having prematurely discontinued the treatment and still continuing the trial
- Post-study^[a]: from the latest between last trial drug intake plus 29 days, ‘date of trial completion’ (from the Trial Completion page of the eCRF) plus one day and ‘date of Informed Consent in extension trial’ plus one day (if applicable). This period is not created if date of first trial drug intake in extension trial is before last trial drug intake plus 28 days

^[a] This period is optional insofar as it does not necessarily exist for all patients.

^[b] In addition, a residual effect period of 7 days will be used for safety analyses to more closely reflect the period of time after the last trial drug intake when measurable drug levels or pharmacodynamic effects are still likely to be present.

All analyses will be based on the planned treatment group (Placebo or Nintedanib 150mg bid) as randomised by IRT.

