7.3 PLANNED ANALYSES

The efficacy and safety analyses will be conducted on the treated set (TS), which consists of patients who are randomized to a treatment group and receive at least one dose of study medication. There will be two co-primary analysis populations: the first will comprise all patients from the treated set (the overall population); the second will comprise all patients from the treated set with HRCT with UIP-like fibrotic pattern only.

The primary assessment of benefit-risk of nintedanib in patients with PF-ILD will be based on efficacy and safety data over 52 weeks (including data from part A only); assessments performed within the first 52 weeks (time-windowing rules will be defined in the TSAP) will be used.

The primary analysis is a random coefficient regression (random slopes and intercepts) model including baseline FVC (mL) and HRCT pattern (except for the analyses on the co-primary analysis population assessing only patients with HRCT with UIP-like fibrotic pattern only) as covariates.

Efficacy and safety data over the whole trial (including data from part A and part B) will be reported descriptively only. Data collected in Part B of the trial and available at the time of the primary analysis data cut-off will be reported after the first database lock. Selected analyses will be repeated after the final database lock and will include data collected until the end of the trial.

All analyses will be based on the treatment group (nintedanib 150 mg bid or placebo) as randomized by IRT.

Although there is no per protocol data set in the study, reasons for important protocol violations will be specified in the Trial Statistical Analysis Plan (TSAP). Patients with important protocol violations will be identified at Blinded Review Planning Meetings and listed in the CTR.

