	B2	
Informed consent given too late
 
eCRF date of informed consent is after date of Visit 1
 
Automatic IPD
 
Additional note: Signature of the wrong IC version, and later signature of the correct one will also be part of this IPD category. This can however only be determined via a manual process.
	None
	B3	
Informed consent not given or withdrawn for optional HRCT but optional HRCT done
 
According to HRCT database and eCRF page informed consent for optional HRCT
 
Manual IPD
	None
C	Trial medication and randomisation		
	C1	
Incorrect trial medication taken between baseline and Week 52
 
Medication taken (between randomisation and Week 52) that is not matching the treatment a patient was randomised to.
 
This can only be determine after unblinding. Programming support for listing generation needed, but a manual allocation process.
 
Additional note: In the CTR Table only the deviation itself will be shown, additional information (e.g. dose level, time point, duration of the wrong medication intake, etc) will be part of a listing.
	None
	C2	
Randomisation not followed
 
The wrong medication kit is given, leading to the patient taking treatment different from the one randomised by IRT at time of randomisation (Visit 2).
 
This can only be determine after unblinding. Programming support for listing generation needed, but a manual allocation process
 
Additional notes: This is only an IPD if the medication error leads to an actual treatment switch.
	None

Table 6.2: 1 Important protocol deviations (continued)

Category/Code	Description	Requirements	Excluded from
C3	Overall compliance between randomisation and Week 52 not between 80% and 120% inclusive (or noncompliance based on investigator assessment)	In case calculated overall compliance is missing: If the answer to the question "Did the patient take trial medication as instructed?" of the eCRF is "No" at at least one of the visits where the compliance cannot be calculated, then an IPD will be flagged. Otherwise no IPD although calculated overall compliance is missing. Automatic IPD with review of MQRM listings	None
C4	Trial medication not interrupted when ALT or AST \geq 5 fold ULN	Based on eCRF dose interruption and adverse event pages between first drug intake and and Week 52 Manual IPD	None

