6.3 PATIENT SETS ANALYSED

- Screened set (SCS):
 - This patient set includes all patients having signed informed consent.
- Randomised set: (RS)
 - This patient set includes all randomised patients, whether treated or not.
- Treated set (TS):
 - This patient set includes all randomised patients who received at least one dose of trial medication. The TS also reflects the “the overall population” for the analyses and is considered as one of the two co-primary populations.
 - The subpopulation of patients with “HRCT with UIP-like fibrotic pattern only” (actual HRCT pattern as documented in the eCRF) is considered as the second co-primary population.
 - The subpopulation of patients with “other HRCT fibrotic patterns” (actual HRCT pattern as documented in the eCRF) is referred to as complementary population
- PK set (PKS)
 - This patient set includes those patients in the TS with at least one valid plasma concentration available

Please note: Details on which set or population is used for which analysis and output can be found in this statistical analysis plan.

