7.8 SAFETY ANALYSIS

All safety analyses will be performed on the treated set. Particular focus will be given to evaluations over the 52 week period (Part A of the study).

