7.8.1 Adverse events

Unless otherwise specified, the analyses of adverse events will be descriptive in nature. All analyses of AEs will be based on the number of patients with AEs and NOT on the number of AEs.

For analysis multiple AE occurrence data on the eCRF will be collapsed into an AE provided that all of the following applies:

- All AE attributes are identical (LLT, intensity, action taken, therapy required, seriousness, reason for seriousness, relationship, outcome, AESI; CTCAE if applicable)
- The occurrences were time-overlapping or time-adjacent (time-adjacency of 2 occurrences is given if the second occurrence started on the same day or on the day after the end of the first occurrence).

For further details on summarization of AE data, please refer to (7, 8).

The analysis of adverse events will be based on the concept of treatment emergent adverse events. That means that all adverse events occurring between first drug intake until last drug intake + 28 days (and + 7 days as sensitivity analysis) will be assigned to the randomised treatment.

All adverse events occurring before first drug intake will be assigned either to 'screening' or 'post-randomisation' (for listings only).

All adverse events occurring after last drug intake + 28 days (and + 7 days as sensitivity analysis) will be assigned to 'post-treatment' or 'follow-up' or 'post-study' (for listings only). All adverse events occurring between the start of an interruption of trial medication and the

end of interruption of trial medication will be assigned to 'off-treatment' period in the listings. For details on the treatment definition, see [Section 6.1](#).

According to ICH E3 ([10](#)), AEs classified as 'other significant' need to be reported and will include those non-serious and non-significant adverse events with (i) 'action taken = discontinuation' or 'action taken = reduced', or (ii) marked haematological and other lab abnormalities or lead to significant concomitant therapy as identified by the Clinical Monitor/Investigator at a Medical Quality Review Meeting.

Adverse events related to gastrointestinal perforation and hepatic injury will be considered as protocol-specified AEs of special interest (AESIs), and ticked as such in the eCRF.

Table 7.8.1: 1 Protocol-specified AESI

Protocol-specified AESI	AE type
Gastrointestinal perforation	AEs established for other tyrosine kinase inhibitors as possible adverse reactions
Hepatic injury	Other AEs of interest

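### Safety data stay in the randomised arm even for patients the SAP foresees taking the other drug, so if such cases occur, events arising on that drug are tabulated under the wrong arm; the effect is small and conditional

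*SAP*

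**What the plan says.** Protocol 7.3, which covers efficacy and safety together, sets one rule: "All analyses will be based on the treatment group (nintedanib 150 mg bid or placebo) as randomized by IRT". SAP 6.1 repeats it: "All analyses will be based on the planned treatment group (Placebo or Nintedanib 150mg bid) as randomised by IRT". SAP 7.8.1 carries it to harm, where treatment-emergent events "will be assigned to the randomised treatment". SAP 7.8 names the analysis set: "All safety analyses will be performed on the treated set". SAP 6.3 defines that set by a first dose, without asking which drug the dose was: "This patient set includes all randomised patients who received at least one dose of trial medication".

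The SAP also expects that some patients may take the other drug. Table 6.2: 1 in section 6.2 has two categories for this:

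- C1: "Medication taken (between randomisation and Week 52) that is not matching the treatment a patient was randomised to".
- C2: "The wrong medication kit is given, leading to the patient taking treatment different from the one randomised by IRT at time of randomisation" (Visit 2). It counts only where the error ends in a real change of treatment.

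Both can be established only after unblinding, and for both the exclusion column reads None. Under C1 the report table shows only the deviation, and a listing gives details such as dose level, time point and duration of the wrong intake. C2 carries no such note on details.

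**The concern.** Grouping as randomised is right for the efficacy analyses, which follow an intent-to-treat principle. Safety tables ask a different question: what happened to patients while they were on a given drug. If a patient randomised to placebo is taking nintedanib when an event starts, the plan books that event to placebo, and the reverse for a patient randomised to nintedanib.

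Mixing the arms pulls the expected difference towards zero, which is the non-conservative direction for harm. It reaches the adverse event tables, the incidence rates, ratios and differences of SAP 7.8.1.5, and the liver elevation outputs of SAP 5.4.4 and 7.8.2. The two protocol-specified events of special interest, gastrointestinal perforation and hepatic injury, may be uncommon, and there a single patient in the wrong column is visible.

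The SAP treats a parallel error differently. When the HRCT stratum used at randomisation was wrong, SAP 4.3 and 7.4.1 analyse the patient by the pattern in the eCRF. SAP 7.4.2.2.2 adds a sensitivity analysis if discrepancies exceed 3%. A wrong stratum is corrected; a wrong drug is not, even in safety tables.

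**Working it through.** **Step 1: is there an exception for safety?** Protocol 7.3, SAP 6.1 and SAP 7.8.1 agree and contain none. Three features might look like one but are not:

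- The 7-day residual period in SAP 7.8.1 changes the time window and keeps the arm: "and + 7 days as sensitivity analysis) will be assigned to the randomised treatment".
- The actual-dose outputs in SAP 5.4.3.1 separate 100 mg from 150 mg, not nintedanib from placebo.
- The exposure dataset in SAP 9.6.1 rests on administration as planned and documented in the eCRF, and sets no rule for the arm.

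**Step 2: how much wrong exposure does C2 imply?** C2 is tied to the Visit 2 kit. Protocol 4.1.4 dispenses one wallet at Visit 2 (30 days plus 5 reserve). Protocol 4.1.6 gives 70 capsules per wallet, so 70 / 2 per day = 35 days. IRT assigns medication again at Visit 4 (day 29) and at later dispensing visits. A C2 patient with correct kits afterwards would take the other drug for about 28 to 35 days, or 28/365 = 7.7% to 35/365 = 9.6% of the year. Taking only the other drug to Week 52 needs repeated wrong dispensing at Visits 2, 4, 6, 7 and 8. Otherwise the patient must stop treatment during the first wallet.

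**Step 3: size.** The plan states no figure to reproduce.

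Inputs:

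- 300 patients per arm (protocol 3.1).
- IPF rates from protocol 1.2: diarrhoea 62.4% vs 18.4%; AST and/or ALT at least 3 times ULN 5.0% vs 0.7%.
- Number switched: not in the documents, so assumed at 0 to 15 per arm (0% to 5%), each on the other drug throughout.

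With a share m of each arm switched, the tabulated difference is

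[pN(1−m) + pP·m] − [pP(1−m) + pN·m] = (pN − pP)(1 − 2m).

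For diarrhoea, 0.44 × (1 − 2m) gives:

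- m = 0: 44.0 points
- m = 0.5%: 0.44 × 0.99 = 43.6 points
- m = 1%: 0.44 × 0.98 = 43.1 points
- m = 2%: 0.44 × 0.96 = 42.2 points
- m = 5%: 0.44 × 0.90 = 39.6 points

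For liver enzymes with k switched per arm, each rate is ((300 − k)·p_own + k·p_other)/300:

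| k per arm | Nintedanib | Placebo | Ratio |
|---|---|---|---|
| 0 | 5.00% | 0.70% | 7.14 |
| 1 | (299×5.0 + 0.7)/300 = 4.99% | (299×0.7 + 5.0)/300 = 0.71% | 6.98 |
| 3 | 4.96% | 0.74% | 6.67 |
| 9 | 4.87% | 0.83% | 5.88 |
| 15 | 4.79% | 0.92% | 5.23 |

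For a rare event, one misplaced patient is 1/300 = 0.33 points in the overall population. With 200 UIP-like and 100 other-pattern patients per arm (protocol Table 7.7: 1), it is 1/200 = 0.50 and 1/100 = 1.0 points in those tables.

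**The case against.** The best case for leaving the plan alone has four parts.

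- **C2 is not whole-trial crossover.** This stands. A reader might infer that C1 and C2 patients have their events charged to a drug they never took. That is true only of a patient whose every dose was of the other treatment. For a one-wallet error, only events during or soon after the wrong intake are misplaced. A rule that moved every C2 patient to the other arm could put someone with about 4 weeks of wrong drug and 48 weeks of randomised drug in the wrong column.
- **The figures are ceilings.** This also stands. They apply full-trial rates to every affected patient, in both arms at once, at assumed switch rates. They do not estimate a bias in this trial.
- **Cases can be traced.** Largely true for C1, through its listing. Read literally, a C2 patient also meets the C1 wording, but the SAP does not say the C1 listing covers C2. Tracing a case does not correct a table.
- **No inference depends on it.** True. Protocol 7.3.4 makes safety descriptive, without hypothesis tests. The rule is consistent across both documents, so there is no contradiction to resolve. But descriptive tables still feed the benefit-risk assessment, and the plan gives no reason for ignoring a known drug error in them.

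**Conclusion.** The point holds as a minor, conditional improvement. As written, any patient who takes the other drug has all safety data tabulated under the randomised arm, and nothing planned corrects this. In expectation the safety difference shrinks; a single case can move a comparison either way or not at all.

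Even at an assumed 2% of each arm fully switched, the diarrhoea difference moves by only 44.0 − 42.2 = 1.8 points. Ratios for uncommon events move more in relative terms: 7.14 to 6.98 for liver enzymes with one switched patient per arm. These sizes rest on the IPF rates carrying over, equal switching in both arms and wrong drug throughout exposure. With no switches the effect is nil, and the documents do not say whether any occurred.

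Two stronger readings are unsupported. The documents do not show that safety results are materially biased. Efficacy is not affected by this point, because analysis as randomised is appropriate there.

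**What to change.** Keep efficacy as randomised. Add to SAP 6.1 and 7.8, and to protocol 7.3, a rule for safety tables:

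- Assign a patient to the treatment received only if every dose taken was of the other treatment, whether flagged C1 or C2. The patient's whole time at risk in SAP 7.8.1.5 moves too.
- Keep patients who took both treatments, and all their time at risk, in the randomised arm. List their adverse events and liver elevations with the drug being taken at onset, and extend the C1 listing explicitly to C2.

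A lighter alternative leaves the main tables alone and pre-specifies an as-treated safety sensitivity table, triggered by any C1 or C2 case. Either rule should be fixed before unblinding, because the cases become known only afterwards.

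The cost is one actual-treatment variable and a few sentences; the affected patients are already to be identified. The downside of the main option is that safety and efficacy denominators may differ by a few patients, which a footnote can explain.

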6.1.1 Over 52 weeks

For efficacy and safety analyses over 52 weeks (Part A), data from first drug intake up to ≤ 372 days after first drug intake will be considered. See [Table 6.1.1: 1](#) for details about analysis periods for Part A according to the type of endpoint.

Table 6.1.1: 1 Summary of analysis periods over 52 weeks (Part A) according to the type of endpoint or analysis

Type of analysis	Analyses / Endpoints	Studied period	
		Start date ^[2]	End date ^[1]
Efficacy analyses over 52 Weeks ^[2]	
 Analyses on all endpoints listed in Sections 5.1.1, 5.1.2 and 5.1.3.1 of the CTP 	Date of first drug intake	Date of last measurement before or at 52 Weeks (≤ 372 days after first drug intake)
On-treatment efficacy analyses over 52 Weeks	
 Annual rate of decline in FVC in ml over 52 weeks, including only data until end date of studied period 	Date of first drug intake	Date of last trial drug intake OR Week 52 time-point (≤ 372 days after first drug intake), whichever occurs first
Descriptive analyses over 52 Weeks	
Absolute change from baseline in:
 
 FVC (ml) FVC (% of predicted) DLCO (% of predicted) Vital signs K-BILD L-PF PF-IQOLS 
Relative change from baseline in :
 
 FVC (% of predicted) 	Date of first drug intake	Date of last measurement before or at 52 Weeks (≤ 372 days after first drug intake)
Extent of exposure analysis over 52 weeks	See Section 5.4.3	Date of first drug intake	
If day of last drug intake < 372 days after first drug intake
 
 Date of last drug intake 
Else, if day of last drug intake \geq Day 373:
 
 Date of first drug intake + 372 days
Safety survival analysis	
Time to
 
 first liver enzyme elevation (for all definitions mentioned in Section 5.4.4) first onset of adverse event with additional information collection (diarrhoea, bleeding, ILD) 	Date of first drug intake	
If day of last drug intake < 372 days after first drug intake:
 
 Date of last drug intake + 28 days 
If day of last drug intake ≥ 373:
 
Date of first drug intake + 372 days

	
Time to
 
 first dose reduction first treatment interruption premature treatment discontinuation 	Date of first drug intake	
If day of last drug intake < 372 days after first drug intake:
 
 Date of last drug intake 
If day of last drug intake ≥ 373:
 
 Date of first drug intake + 372 days
On-treatment safety analysis over 52 weeks	
 Adverse events Laboratory data Vital signs 	Date of first drug intake	
If day of last drug intake < 372 days after first drug intake:
 
 Date of last drug intake + 28 days 
If day of last drug intake ≥ 373:
 
 Date of first drug intake + 372 days

^[1] End date is included.^[2] Date of randomisation and date of first drug intake should be identical. If there are discordances between these dates on patient level, date of first drug intake will be used.

6.1.2 Over the whole trial

For efficacy and safety analyses over the whole trial period (Part A and Part B), data from first drug intake up to the last visit in the trial will be considered. Please see Table 6.1.2: 1 for details about analysis periods over the whole trial (Part A + Part B) according to the type of endpoint. For the main analysis only data collected over the whole trial available at the time of data cut-off for DBL1 will be considered, whereas all data collected within the trial will be considered and reported for the final analysis.

Table 6.1.2: 1 Summary of analysis periods over the whole trial (Part A and Part B) according to the type of endpoint or analysis

Type of analysis	Analyses / Endpoints	Studied period	
		Start date ^[2]	End date ^{[1][4]}
Efficacy analyses	Analyses on all endpoints listed in Sections 5.1.3.2 of the CTP	Date of first drug intake	Date of last measurement up to the last follow-up visit (included) or last contact date (as defined in Section 5)
Descriptive analyses over the trial period	Absolute change from baseline in: 
• FVC (ml)• FVC (% of predicted)• DLCO (% of predicted)• Vital signs Relative change from baseline in : 
• FVC (% of predicted)	Date of first drug intake	Date of last measurement up to last follow-up visit (included)
Efficacy survival analysis	Time to all-cause mortality (over the trial period)	Date of first drug intake	Last contact date (as defined in Section 5)
Extent of exposure analysis overall	See Section 5.4.3	Date of first drug intake	Date of last drug intake
Safety survival analysis ^[3]	Time to 
• first liver enzyme elevation (for all definitions mentioned in Section 5.4.4)• first onset of adverse event with additional information collection (diarrhoea, bleeding, ILD)	Date of first drug intake	Date of last drug intake + 28 days
	Time to 
• first dose reduction• first treatment interruption• premature treatment discontinuation	Date of first drug intake	Date of last drug intake
On-treatment safety analysis overall ^[3]	
• Adverse events• Laboratory data• Vital signs	Date of first drug intake	Date of last drug intake + 28 days

[1] End date is included.

[2] Date of randomisation and date of first drug intake should be identical. If there are discordances between these dates on patient level, date of first drug intake will be used.

[3] Patients who switch to the extension study will only be evaluated until date of last drug intake in this study. The residual effect period will not apply, as patients will receive continuous treatment.

[4] For the main analysis only data collected over the whole trial available at the time of data cut off for DBL1 will be considered, whereas all data collected within the trial will be considered and reported for the final analysis.

